## 1. Background and Rationale

Lipodystrophy is a rare condition characterised by a paucity of body fat due to the absence or dysfunction of adipocytes (fat cells). It can be inherited or acquired in origin and can result in a total (generalised lipodystrophy) or partial loss of adipose tissue (partial lipodystrophy). It has been estimated that there are 1.3–4.7 cases of lipodystrophy per million people worldwide (Dhankhar 2017). Due to the lack of fat storage capacity, excess lipid accumulates in other tissues such as the liver, pancreas and muscle where it impairs insulin action and contributes to the pathogenesis of several metabolic disorders including diabetes, non-alcoholic fatty liver disease and pancreatitis.

As fat transplantation or correction of the underlying genetic defect have yet to become viable therapeutic options, current therapeutic approaches focus on preventing and managing the metabolic complications of lipodystrophy using standard approaches used to treat obese patients with similar metabolic problems including agents such as metformin, gliptins, statins, fibrates and/or insulin (Brown et al. 2016). Advice for the dietary management of lipodystrophy is based on the evidence available from studies in patients with type 2 diabetes, cardiovascular disease and high triglycerides (Stears & Hames 2014). The general advice for all patients with lipodystrophy includes calorie and fat restriction (Brown et al. 2016). However, this approach is currently based on clinical experience rather than experimental evidence. Four case reports on patients with congenital generalised lipodystrophy describe improvements in blood glucose and triglycerides after restricting calorie and fat intake (Joannie et al. 2017; Kazlauskaitė et al. 2001; Santos & Chvng 2017; Keenan et al. 1980), however there are currently no published studies.

Our group runs the only specialist NHS England designated service for patients with lipodystrophy at CUHFT (Cambridge University Hospitals Foundation Trust; website <https://www.cuh.nhs.uk/national-severe-insulin-resistance-service>). Our current dietetic approach includes specialist input from two dietitians who have been working with the multidisciplinary team since its inception in 2012. They focus on assessing current energy intake and macronutrient balance, and then attempt to assist patients in significantly reducing total energy intake. In general this is very helpful in improving the metabolic consequences of lipodystrophy – specifically NAFLD, dyslipidaemia (particularly hypertriglyceridaemia) and glycaemic control – in patients who adhere to the dietary advice. However, dietary compliance remains very challenging as the lipodystrophy itself leads to total or relative deficiency of leptin, a key hormone in the regulation of appetite. Lack of leptin is well known to promote food intake, so our patients have to work very hard to adhere to dietary calorie restriction. We also currently lack published evidence to support our approach, hence our interest in undertaking a formal study to document the impact of dietary calorie restriction. However, we and others have shown that severely limiting calorie intake by means of bariatric (weight loss) surgery is safe and highly effective in alleviating metabolic disease in lipodystrophic patients (Melvin et al. 2017; McGrath & Krishna 2006; Utzschneider & Trencé 2006; Ciudin et al. 2011; Kozusko et al. 2015; Grundfest-Broniatowski et al. 2017). Unfortunately access to bariatric surgery remains limited in the UK currently and it is an expensive, ‘fairly radical’ option.

Recent results from the DIRECT study (Lean et al. 2017) reported substantial improvements in HbA1c, triglycerides and a reduction in antidiabetic medication for people with type 2 diabetes that followed a structured weight management programme. The DIRECT study recruited people that had been diagnosed with type 2 diabetes within the last 6 years and who were not receiving insulin, they were then randomised into two groups; one group were provided with a weight management

programme while the other received best practice by care guidelines. The weight management programme comprised of a total diet replacement (825–853 kcal/day formula diet for 3–5 months), stepped food reintroduction (2–8 weeks), and structured support for long-term weight loss maintenance. Diabetes remission was achieved in 46% of the intervention group compared to 4% in the control group (Lean et al. 2017). This approach has now been validated in a series of carefully planned and run studies and is being rolled out into general practice in the UK currently. We typically advise calorie restriction to a similar level in our patients so would like to formally assess this intervention in a study in our lipodystrophic patients.

The fact that this dietary intervention is very likely to rapidly alleviate insulin resistance in patients with FPLD – based on what has been seen in obese patients with T2DM in response to LEDs and in FPLD patients in response to bariatric surgery (Melvin et al. 2017) – also provides a unique opportunity to evaluate underlying mechanisms of insulin resistance in these patients. Despite decades of research (Petersen & Shulman 2018) the molecular mechanisms responsible for human insulin resistance remain unclear. Suggested defects include diacylglycerol (DAG) or ceramide accumulation and subsequent activation of PKCtheta in skeletal muscle (PKCepsilon in liver) which is in turn proposed to phosphorylate the insulin receptor. However, considerable debate continues about this and other hypotheses. The fact that we expect insulin resistance to be rapidly and reliably reversed in compliant participants offers a rare opportunity to obtain muscle and adipose samples before and then during the intervention. The samples will then be analysed a) histologically to assess lipid accumulation and inflammation, b) genetically to document changes in gene (mRNA) expression, c) for changes in protein expression and phosphorylation and d) metabolically in order to evaluate changes in DAGs and ceramides as well as other candidate lipid intermediates.

## 2. Summary of study

To evaluate the therapeutic efficacy and metabolic impact of a low energy diet (LED) in people with familial partial lipodystrophy and diabetes. Participants will be provided with a LED (total diet replacement) for 12 weeks, before the introduction of a stepped food transition as was done by Lean et al (Lean et al. 2017) in patients with type 2 diabetes. Metabolic effects will continue to be assessed for one year. In order to better understand why this intervention changes insulin sensitivity, we will also collect adipose and muscle tissue samples at baseline and 12 weeks into the intervention in participants willing to have these procedures performed. The original study by Taylor et al (Lim et al. 2011) suggested that insulin resistance was significantly improved by this time point so we anticipate a similar response in our patient cohort. These samples will be used for histological, metabolite, gene expression and protein expression analyses.

## 3. Objectives and Outcome Measures

### 3.1 Aims

- To determine whether following a LED dietary intervention in people with familial partial lipodystrophy will improve:
  - Glycaemic control
  - Hypertriglyceridaemia
  - Hepatic fat content

- Insulin sensitivity
- To assess whether there is any change in quality of life, anxiety and depression at the end of the intervention
- To assess metabolic control up until one year post intervention

### 3.2 Primary Endpoint

A reduction in HbA1c at 12 weeks

### 3.3 Secondary Endpoints

- A reduction in HbA1c at 1 year
- A reduction in fasting glucose at 12 weeks and 1 year
- A reduction in triglycerides at 12 weeks and 1 year
- A reduction in liver fat at 12 weeks and 1 year
- A reduction in pancreatic fat at 12 weeks and 1 year
- An increase in insulin sensitivity (based on an oral glucose tolerance test (OGTT) at 12 weeks and 1 year
- An improvement in quality of life, anxiety and depression scores (as measured by PHQ9, GAD7 and EQ-5D-3LQOL)
- A reduction in antidiabetic medication use at 12 weeks and 1 year

## 4. Recruitment

Patients with partial lipodystrophy referred to our centre and who meet the inclusion criteria will be invited to take part in the study. A computerised search of medical records of patients attending the National Severe Insulin Resistance (NSIR) Service will be conducted by the clinical care team and potentially eligible participants will be invited to participate in the study. Potential participants will be invited at clinical appointments, via telephone calls, letters or email. They will be provided with an invitation letter and a patient information sheet along with contact details of the study team. Potential participants will be contacted to answer queries and ascertain interest.

### 4.1 Inclusion criteria

- Familial Partial Lipodystrophy
- Age  $\geq$  18 yrs
- T2DM
- Willingness to check daily blood sugars
- HbA1c between 53mmol(7%)- 108 mmol(12%)
- Weight stable for 3 months
- Capacity to consent

### 4.2 Exclusion criteria

- Pregnancy
- Untreated thyroid dysfunction (patients who have been euthyroid on medication for at least 3 months can be included)
- Use of medication that adversely affects diabetes control (e.g. steroids/ immunosuppressants/ certain antipsychotics)
- Incapacity to give informed consent

- History of an eating disorder/ purging behaviour
- Previous gastric bypass/ banding
- Use of leptin therapy
- Untreated proliferative retinopathy

#### 4.3 Screening

Once potential participants have confirmed they are interested in participating in the study a screening visit appointment will be booked via the telephone and a screening proforma will be completed (see Appendix A). A member of the research team will explain the diet intervention and the study plan to the participant. Participants will be asked about their willingness to follow the diet plan. Participants will be asked to keep a food diary for 7 days whilst on their normal diet before their baseline appointment.

#### 4.4 Sample

20- 30 participants will be recruited to participate.

### 5. Study Intervention

Usual food will be replaced by a total diet replacement (TDR). This will come as a formula food which comes as sachets of powder and is reconstituted with water, this is consumed with ample liquids (of approximately 3L) for 12 weeks and a fibre supplement will be prescribed. The TDR will be a commercial micronutrient-replete liquid formula diet providing approximately 800-853 cals, and consists of formulas and shakes. Following 12 weeks of TDR a stepped food reintroduction will be commenced in which food will slowly be reintroduced back into the diet over 6 weeks. The weight loss maintenance phase follows food reintroduction and aims to maintain the changes to eating and activity behaviours that have been made over the previous months. If participants' metabolic control worsens due to non-compliance during the maintenance phase a rescue plan can be used, in which participants are supported to incorporate the TDR again.

### 6. Study Design

Participants that are eligible and consent to take part in the study will be given an appointment to attend the Cambridge Clinical Research Centre (CCRC) at Addenbrooke's Hospital to participate in the study.

Participants will be commenced on a 12 week total diet replacement after which they will follow a stepped food reintroduction phase (weeks 13-18) and will then be followed up through a weight loss maintenance phase (weeks 19-52). Participants will be monitored throughout the year and will be seen for investigations and study procedures at the Clinical Research Facility.

- Total Diet Replacement phase - Participants will be seen face to face for metabolic investigations at baseline, week 4, week 8 and week 12. During this time the participants will be closely monitored with weekly phone calls, which will be increased if needed – this is mainly to avoid hypoglycaemia following the introduction of the LED.
- Stepped Food Reintroduction - Participants will be seen at week 16 for metabolic investigations and will be closely monitored with two-weekly phone calls which will be increased if needed to

maintain optimal glycaemic control. At the start of stepped food reintroduction orlistat 120mg three times a day will be prescribed and commenced, in line with standard practice.

- Weight loss maintenance - Participants will be seen at week 24, 36 and 52 and from week 24 will be followed up with four-weekly phone calls which will be increased if needed.

See Appendix B for a schedule of investigations and procedures.

## 7. Study Procedures

### 7.1 Clinical Assessment

All participants will undergo baseline clinical assessment which includes a detailed medical, family and social history. Clinical information will be recorded in a case record file identified only by a unique study identifier that will have been assigned to that participant.

### 7.2 Consent Procedure

Individuals who fulfil the inclusion criteria and are agreeable to study participation will attend the research facility at a scheduled date and time. A unique identifier code will be assigned to the participant at this point. A named investigator of the research team will obtain written informed consent prior to the initiation of any study procedures.

### 7.3 Anthropometric measures

- Weight measurement

Study participants will have their weight measured on a digital equilibrated scale. The measurements will be taken after the participant has been asked to void. Participants will be weighed in their clothing with their shoes off and in bare feet or socks. Measurements will be recorded to the nearest 0.1Kg.

- Height measurement

Study participants will have their height measured using a stadiometer. This measurement will be taken in bare feet or socks. Participants will be asked to stand upright with their heels, buttocks and occiput touching the backboard of the stadiometer. The measuring arm of the stadiometer will be brought down to the top of the subject's head. Height is recorded to the nearest 0.1cm.

- Waist circumference

A non-stretch tape measure will be used to measure waist circumference. The measurement will be taken with the subject in a standing position with the abdomen relaxed, the arms at the sides and the feet together and breathing normally. The measurer faces the subject and places a measuring tape around the subject in a horizontal plane, at the mid-point between the lowest rib and the supra iliac crest. The measurement should be taken at the end of a normal expiration, ensuring the tape is taut around the subject's waist, without compressing the skin. Waist circumference measurements will be taken in duplicate and values will be recorded to the nearest 0.1cm. The mean value of both measurements will be recorded as the waist circumference.

## 7.4 Venepuncture

The participant will undergo venous catheter insertion and blood sampling with fasting samples being sent for baseline biochemical measurements at the biochemistry laboratory, Cambridge University Hospital. Serum and plasma samples will also be retained for more specialised assays. Participants will be asked to fast prior to testing from 10pm on the night prior to study.

## 7.5 Magnetic Resonance Imaging/ Magnetic Resonance Spectroscopy

Magnetic Resonance Imaging and spectroscopy studies will be undertaken to image subcutaneous and abdominal fat depots and quantify the triglyceride (TG) content in liver, pancreas and skeletal muscle. TG accumulation is strongly associated with insulin resistance and we anticipate this to be alleviated by the diet intervention. These will be taken at baseline, 3 months, 6 months and 1 year. These are non-invasive procedures. Studies will be conducted in the Wolfson Brain Imaging Centre (WBIC).

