## 7.7 Indirect Calorimetry

Indirect Calorimetry will be undertaken to assess Basal Metabolic Rate (BMR) using a Gas Exchange Measurement instrument. BMR typically falls with weight loss in obese patients so we would like to see if this also happens in patients with FPLD. Participants are advised to avoid any vigorous exercise and caffeine on the day prior to calorimetry. A standardised evening meal based on their weight and predicted or known (DEXA) body composition will be provided to the participant on the day prior to calorimetry followed by overnight fasting. The measurement will be undertaken by the technician at 7.30 am in the participant's own room at the WTCRF.

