| Waist & Hip              |   | ✓          |        |        |        |            | ✓      |        |        |        | ✓     |        |            | ✓      |  |  |  |  |  |  |  |
| Blood Pressure           |   | ✓          |        |        |        |            | ✓      |        |        |        | ✓     |        |            | ✓      |  |  |  |  |  |  |  |
| Blood Glucose readings   |   | ✓          | ✓      | ✓      | ✓      | ✓          | ✓      | ✓      | ✓      | ✓      | ✓     | ✓      | ✓          | ✓      |  |  |  |  |  |  |  |
| Medication Review        |   | ✓          | ✓      | ✓      | ✓      | ✓          | ✓      | ✓      | ✓      | ✓      | ✓     | ✓      | ✓          | ✓      |  |  |  |  |  |  |  |
| Oral Glucose Test        |   | ✓          |        |        |        |            |        |        |        |        |       |        |            |        |  |  |  |  |  |  |  |
| GEM                      |   | ✓          |        |        |        |            |        |        |        |        |       |        |            |        |  |  |  |  |  |  |  |
| MRI Liver & Pancreas     |   | ✓          |        |        |        |            |        |        |        |        |       |        |            |        |  |  |  |  |  |  |  |
| DEXA                     |   | ✓          |        |        |        |            |        |        |        |        |       |        |            |        |  |  |  |  |  |  |  |
| Fat Biopsy (optional)    |   | ✓          |        |        |        |            |        |        |        |        |       |        |            |        |  |  |  |  |  |  |  |
| Muscle Biopsy (optional) |   | ✓          |        |        |        |            |        |        |        |        |       |        |            |        |  |  |  |  |  |  |  |
| Urine sample             |   | ✓          |        |        |        |            | ✓      |        |        |        | ✓     |        |            | ✓      |  |  |  |  |  |  |  |
| Questionnaires           |   | ✓          |        |        |        |            |        |        |        |        |       |        |            | ✓      |  |  |  |  |  |  |  |
| Dietary Phase →          | Food Reintroduction (Weeks 13-18)         |            |        |        |        |            |        |        |        |        |       |        |            |        |  |  |  |  |  |  |  |

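### Does the visit schedule in Appendix B leave the 12-week and 1-year OGTT and MRI endpoints, and the second biopsies, without any measurement?

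*Protocol*

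**What the plan says.** The prose gives times for three of the four procedures.

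- **MRI/MRS.** Section 7.5 sets four occasions: "These will be taken at baseline, 3 months, 6 months and 1 year". Two endpoints in Section 3.3 depend on these scans: "A reduction in liver fat at 12 weeks and 1 year" and "A reduction in pancreatic fat at 12 weeks and 1 year".
- **OGTT.** Section 3.3 lists "An increase in insulin sensitivity (based on an oral glucose tolerance test (OGTT) at 12 weeks and 1 year". A change also needs the baseline test, so three tests in all.
- **Biopsies.** Section 2 says the team will "collect adipose and muscle tissue samples at baseline and 12 weeks into the intervention in participants willing to have these procedures performed". They are optional, no 1-year biopsy is mentioned, and they are not among the endpoints in Sections 3.2 and 3.3.
- **Calorimetry.** Section 7.7 gives a purpose but no times: "BMR typically falls with weight loss in obese patients so we would like to see if this also happens". It is not a listed endpoint either.

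Section 6 has face-to-face visits at baseline and weeks 4, 8, 12, 16, 24, 36 and 52, and refers the reader to Appendix B for the schedule of procedures. Appendix B has three panels: weeks 0-12, 13-18 and 19-52.

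**The concern.** Appendix B is the only visit-by-visit schedule in the protocol. Reading along the row "MRI Liver & Pancreas" and its neighbours, one finds a baseline mark and at most one more, in the maintenance panel. Six adjacent rows (OGTT, calorimetry, MRI, DEXA and the two biopsies) have no week-12 mark, although the urine and questionnaire rows just below them do.

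If the printed schedule really looked like this and staff worked from it, the loss would matter. Section 9 describes a before-and-after comparison without a control group, so a missing follow-up value means no estimate at all for that participant. Liver fat, pancreatic fat and insulin sensitivity would have no 12-week change. One maintenance mark could not serve both 6 months and 1 year for MRI. The tissue comparison would have no second sample, and a missed week-12 biopsy or scan cannot be recovered later.

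**Working it through.** No sample-size, power or alpha figure is involved. The check compares counts, then asks whether the counts can be relied on.

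**Step 1. Text against marks** (marks summed over the three panels)

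| Procedure | Occasions in the text | Marks in Appendix B |
|---|---|---|
| MRI | 4 (Section 7.5) | 1 + 0 + 1 = 2 |
| OGTT | 3 (baseline plus two in Section 3.3) | 1 + 0 + 1 = 2 |
| Each biopsy | 2 (Section 2) | 1 + 0 + 0 = 1 |
| Calorimetry | at least 2 implied, no times given (Section 7.7) | 1 + 0 + 0 = 1 |

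The shortfall exists only if each mark in the table as available stands for one planned occasion and none has been lost.

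**Step 2. Are the positions intact?** They are not.

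- In weeks 0-12 the visit ticks fall under weeks 5, 9 and 12; Section 6 says weeks 4, 8 and 12.
- In weeks 13-18 the visit, bloods and urine ticks are in the sixth column, while weight, waist and blood pressure for the same visit are in the seventh. Only five weeks are labelled.
- In weeks 19-52 the bloods ticks are in columns 4, 8 and 14 and the urine ticks in columns 5, 9 and 14, although both describe the same three visits and only ten weeks are labelled.
- The 1-month label stands under Screening and the 2-month label under week 11. No 3-month or 12-month label survives, and those are the times at issue.

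**Step 3. Are the counts intact?** They are not either.

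- Blood glucose readings and medication review each carry 14 ticks in the weeks 13-18 panel, against five labelled weeks: 14 - 5 = 9 too many.
- The same two rows carry 14 ticks in the weeks 19-52 panel, against ten labelled weeks: 14 - 10 = 4 too many.
- Height has a tick in weeks 13-18, its only one after baseline.
- The maintenance face-to-face row has 2 ticks where Section 6 requires 3 (weeks 24, 36, 52). A lone tick among the squares of the telephone row is probably the third, so a mark has changed rows.
- The weeks 0-12 telephone row has 10 squares. Removing the three visit weeks leaves 12 - 3 = 9. This is weaker evidence, since a call in a visit week could be intended.

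Marks have therefore been added, moved between columns and moved between rows.

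**Step 4. What does the pattern of gaps show?** The rows without a week-12 mark form one contiguous block, with complete rows above and below. A failure in reading that block would look like this, and so would a true omission. Nothing in the text separates the two.

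**Step 5. Does the prose contradict itself?** It does not. Twelve weeks in Section 3.3 corresponds to 3 months in Section 7.5, and both sections name 1 year. Section 6 provides visits at weeks 12 and 52. Sections 2, 3.3, 6 and 7.5 together describe a design in which every listed OGTT and MRI endpoint has its measurement, and the biopsies their second time point.

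**The case for a change.** The best counter-argument relies on counts in rows that can be checked. Section 6 gives eight visits. Fasting bloods, weight, waist, blood pressure and urine each show 4 + 1 + 3 = 8 marks, and the face-to-face row reaches 8 once the stray tick is returned to it: 4 + 1 + 2 + 1 = 8. On this view marks were displaced but none disappeared, and a loss would have had to strike the procedure rows while sparing every row that can be verified. The OGTT, MRI and DEXA rows also kept a maintenance mark, so they were not simply wiped out.

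This is a fair point, and it keeps a real omission in the printed appendix possible. It does not establish one. The rows that check out lie outside the block in question, so they say little about a failure confined to that block. The surplus ticks and the height tick show that counts are not preserved throughout, so agreement in some rows cannot be carried over to others. Even on this argument, loss of a block of adjacent rows cannot be excluded.

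One part does stand: Section 7.7 gives no follow-up time for calorimetry, and no later mark is visible. That is a missing detail about an exploratory measure, not a contradiction with a stated endpoint.

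**Conclusion.** The concern does not hold. A shortfall in Appendix B could be asserted only if its mark counts were reliable, and the table shows surplus, displaced and misplaced marks together with missing labels. Damage of that kind is not an error in the plan.

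The prose names all four MRI occasions, both OGTT endpoint times and both biopsy times, without conflict between sections, so none of the three secondary endpoint lines loses its 12-week or 1-year value under the stated design. The endpoint wording could never have covered biopsies or calorimetry, since neither is a listed endpoint. The primary endpoint in Section 3.2 is unaffected in any case: the fasting bloods row has its fourth mark in the weeks 0-12 panel, at week 12.

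This conclusion assumes that the gaps in the six-row block may be reading losses. A look at the original PDF would settle that. If the marks proved absent there too, the result would be an inconsistency between an appendix table and clear prose, not a flaw in the design or the analysis.
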